## SPECIFIC OBJECTIVES

### Primary

To determine the capacity and tolerance to exercise by means of a cardiopulmonary test and to assess the effects and changes after a PRR in patients with BE without CF.

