### Exclusion criteria

- Smokers or former smokers of less than 6 months or with a history of consumption of 15 packs/year.
  - Cystic fibrosis.
  - Active infections (bronchopulmonary aspergillosis, pulmonary tuberculosis).
  - Active tuberculosis.
  - poorly controlled asthma

- Chronic obstructive pulmonary disease.
- Diseases that prevent adequate performance of exercise (neuromuscular pathology or residual injuries)
- Medical diseases that put the individual at risk of a decompensation due to the performance of any physical activity or cardiopulmonary stress test (unstable ischemic heart disease, acute myocardial infarction less than 1 month).
- Pregnancy.
- Mental disorder that prevents the adequate interpretation of the indications or performance of the tests.

- **Study design.**

Prospective and randomized study with consecutive inclusion of patients from the Non-CF bronchiectasis BE monographic clinic of the Virgen Macarena Hospital (Seville). Patients who meet the inclusion criteria will be randomized into two groups: control and intervention, patients will be assigned to each group using a numerical sequence generated by computer until the sample size is obtained.

The control group will receive basic recommendations on physical activity and the intervention group will be included in a mixed respiratory rehabilitation program (combining home and hospital sessions).

**Visit 1:** inclusion of patients with BE who comply with inclusion. Signature of informed consent and randomization of patients.

**Visit 2:** All patients will undergo an initial assessment of the degree of physical activity by means of accelerometers (®Sensewear arm band) for 3 days including weekends, as well as pulmonary function and exercise tolerance tests, stratification of severity according to the E-FACED scales.

\* Control group: written recommendations on performing some physical activity for at least 30 minutes of moderate intensity according to the recommendations of the Spanish Society of Pulmonology and the Andalusian Society of Pulmonology and Thoracic Surgery. (Casilda Olveira, Costa, and Martínez-García 2016) , (C Olveira et al. 2010). A phone call every 15 days to assess the physical activity carried out without talking about exercise or physical activity.

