\* Intervention group: Patients will be included in an 8-week outpatient program with recall sessions led by our physiotherapist once every 2 weeks in the hospital's Respiratory Rehabilitation gym. In the first session, patients will be instructed on how to perform home exercises as well as how to use the Borg scale. A phone call weekly to provide support and general advice about exercise or physical activity.

The program will combine isotonic strength and resistance exercises. Resistance training will consist of bicycle or walking exercises (depending on the availability of each patient), with a progressive increase in distance or time of completion depending on symptom control.

The strength training program will include upper and lower limb exercises that will begin with no load and to which weights will be progressively added depending on the control of symptoms, in 2 sets of 6-8 repetitions:

- Hanger (to work the latissimus dorsi muscle).
- Butterfly (pectoralis major muscle work).
- Neck press (brachial triceps and deltoid work).
- Flexion of legs (work of biceps femoris and gastrocnemius).
- Extension of legs (work of quadriceps femoris): place a weight or ballast. Stretch the leg and raise the thigh
- Exercises with elastic bands: upper and lower limbs. Separate both ends of the tape as much as possible.
- Walking: increase the walking time progressively.
- Bicycle or treadmill: submaximal exercise. Constant pedaling at about 60 rpm with moderate intensity.

Patients will be encouraged to maintain the exercises after the study.

**Visits 3, 4 and 5:** at 8 weeks (time of completion of the rehabilitation programs), 6 months and 12 months, respectively. At the end-of-program and follow-up visits, all the measurements made at the baseline visit will be repeated, as well as the record of exacerbations.

All patients will receive an educational program about their disease as well as an individualized respiratory physiotherapy program including relaxation techniques, secretion management and assessment of nutritional status.

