## Statistical analysis

For the calculation of the sample size, a power of 95% is used, a hypothetical loss rate during the study of 15%, a total of 30 patients per group would be included, enough to demonstrate our hypothesis and find statistically significant differences in the capacity of exercise and the change in physical activity in the two populations.

Statistical analysis was performed using the statistical analysis software IBM SPSS Statistics (SPSS v23, Chicago, IL, USA). For quantitative variables, the values are expressed as mean +/- standard deviation, while in the case of qualitative variables; their values are included as frequency and percentage. The comparison between groups was carried out using the T test for independent samples in the event that the data behaved according to a normal distribution. Otherwise, the Mann-Whitney U test was used for independent samples. The comparison of the effects of respiratory rehabilitation was performed with the Student's t test for related samples when the data follow a normal distribution and the Wilcoxon signed rank test for related samples. In all cases, the minimum level of significance was considered to be  $p < 0.05$ . If statistically significant differences are identified between the different groups studied, "a posteriori" comparison tests will be carried out, such as the Mann-Whitney U test according to application criteria, with the level of significance corrected.

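### The plan has both between-group and within-group tests, attributes the effect of rehabilitation to the within-group ones, and names no variable, visit or test that decides the primary objective

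*Combined protocol and SAP*

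**What the plan says.** The Primary objective has two parts. The first is "To determine the capacity and tolerance to exercise by means of a cardiopulmonary test". The second, which concerns the programme, reads "to assess the effects and changes after a PRR in patients with BE without CF". It gives no variable, visit or contrast. Under Measurement methods and variables, the cycle-ergometry item lists about ten outputs (by our count), among them maximum oxygen consumption, thresholds and the respiratory compensation point, and ranks none of them.

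The Study design text states: "Patients who meet the inclusion criteria will be randomized into two groups: control and intervention". On treatment, "The control group will receive basic recommendations on physical activity", and "All patients will receive an educational program about their disease as well as an individualized respiratory physiotherapy program". Visits 3, 4 and 5 fall "at 8 weeks (time of completion of the rehabilitation programs), 6 months and 12 months, respectively", and "At the end-of-program and follow-up visits, all the measurements made at the baseline visit will be repeated".

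The Statistical analysis section contains four relevant elements:

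- A comparison between groups by independent-samples t test, or Mann-Whitney U if the data are not normal.
- A comparison described as that of the effects of respiratory rehabilitation, by paired t test or Wilcoxon signed rank test.
- A threshold: "In all cases, the minimum level of significance was considered to be" p < 0.05. The next sentence applies a corrected level, by an unnamed method, to a posteriori comparisons made after a significant group difference.
- A sample-size sentence (95% power, 15% loss, 30 per group) that aims at differences between the two populations in both exercise capacity and change in physical activity. The Secondary objectives list physical activity as secondary.

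**The concern.** Randomisation makes the contrast between arms the evidence for the programme. A related-samples test compares an arm with itself, so it also picks up anything that moves both arms: education, physiotherapy, activity advice, repeat testing, regression to the mean. By labelling the paired tests as the ones that address the effect of rehabilitation, the section allows a before-after change to be reported as that effect.

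Separately, several cycle-ergometry outputs measured at three follow-up visits give many possible answers to one primary objective. Nothing in the text available for review says which one decides. If results are mixed, or if the intervention arm improves without differing from control, there is no agreed reading, and the choice could be made after the data are seen.

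**Working it through.** **1. The plan's own figure.** The 30 per group cannot be reproduced, because no effect size, SD or primary variable is given. Allowing for loss, 30 × 0.85 = 25.5, so 25 per arm is used below. At 95% power and an assumed two-sided 0.05, 25 per arm corresponds to a standardised difference of (1.960 + 1.645) × √(2/25) = 1.02. The plan does not state this value, so the 30 is neither confirmed nor refuted.

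**2. Paired test when the programme adds nothing.** Assumption, not in the documents: both arms improve by the same δ, in SDs of change. The paired t statistic in the intervention arm is then noncentral t with 24 degrees of freedom and noncentrality δ√25 = 5δ. It is significant if its absolute value exceeds 2.064. The between-group test of change has true difference zero. The last two columns are from 200,000 simulated trials.

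| δ | Noncentrality | Paired test significant | Between-group test significant | Paired significant, between-group not |
|---|---|---|---|---|
| 0.2 | 1.0 | 16% | 5% | 14% |
| 0.3 | 1.5 | 30% | 5% | 28% |
| 0.4 | 2.0 | 48% | 5% | 46% |
| 0.5 | 2.5 | 67% | 5% | 64% |

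With all 30 per arm evaluable, the paired-test column becomes 19%, 36%, 56% and 75%.

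**3. Several between-group tests at 0.05.** Assumptions, not in the documents: no true difference, normal test statistics with common correlation r, cut-off 1.96, and any significant result may count. Three tests stand for one variable at three visits, or three variables at one visit. The chance of at least one significant result is 1 − E[{Φ((1.96 − √r X)/√(1 − r)) − Φ((−1.96 − √r X)/√(1 − r))}³], with X standard normal. For false benefit only, the second Φ term is dropped.

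| r | Either direction (nominal 5%) | False benefit (nominal 2.5%) |
|---|---|---|
| 0.9 | 8.4% | 4.2% |
| 0.7 | 10.9% | 5.5% |
| 0.5 | 12.5% | 6.3% |

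Three is a modest count. Three variables at three visits, with the same r across variables and across visits, give 14%, 23% and 29% in either direction.

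**4. Does the planned correction help?** It starts only once a group difference is already significant. With two groups there is no further pair of groups to compare, and the sentence does not mention variables or visits. It therefore does not protect the initial tests in step 3.

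**The case against.** The strongest reply is that the plan already has the right test. It specifies an independent-samples comparison, and its sample-size sentence aims at a difference between two populations. That stands. A reader might infer that only within-group tests are planned; the documents do not support this. What remains is that the between-group test is not tied to change from baseline, to a variable or to a visit, while the sentence on the effect of rehabilitation points to the other test.

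A reader might also infer that an uncorrected 0.05 governs every test. It does not: the a posteriori comparisons use a corrected level, though step 4 shows how little that covers.

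Third, the percentages are not estimates for this trial. No rule says that any significant result counts, and the correlations, number of tests and shared improvement are all assumed. That also stands. In particular, it would be wrong to say that the false-benefit rate must exceed 5%: at r = 0.9 with three tests it is about 4%, although still above 2.5%.

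Fourth, 8 weeks is the natural visit, since the programme ends then. Neither the objective nor the analysis section says so, and the variable would still be open.

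Finally, the title calls the programme a pilot. But the sample-size text claims enough patients, at 95% power, to demonstrate the hypothesis. That is a confirmatory aim, and it needs a defined deciding test.

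**Conclusion.** The point holds in this form: two kinds of test are planned, the effect of rehabilitation is attached to the one that does not use the randomised comparison, and no available section names the variable, visit or test that settles the primary objective. This conclusion rests on the text alone.

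The size depends on assumptions. With equal improvement of 0.2 to 0.5 SD in both arms and 25 per arm, relying on the paired test would credit an ineffective programme in 16% to 67% of trials, against 5% for the between-group test. With three uncorrected between-group tests, any of which may count, the error rate is 8% to 13% two-sided, or about 4% to 6% for false benefit against 2.5%, at correlations of 0.9 to 0.5. The actual error rate of this plan cannot be calculated, because the decision rule is missing. It should be settled before outcome data are seen, since a choice made afterwards would not be credible.

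**What to change.** In the Primary objective and the Statistical analysis section, before any outcome data are seen:

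- State that the effect of rehabilitation is judged by the between-group difference in change from baseline in one named cycle-ergometry variable at one named visit, at two-sided alpha 0.05. Maximum oxygen consumption at 8 weeks (Visit 3) is one example; the sponsor may choose another variable or visit, or prespecify a fixed hierarchy.
- State that related-samples tests are descriptive.
- Report other measures and visits as secondary or exploratory, with 95% confidence intervals.
- Align the sample-size sentence with the single primary outcome. It now pairs exercise capacity with physical activity, which the Secondary objectives make secondary.

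This needs no new patients or measurements. The downside is that fewer results can be called confirmatory. A single primary test, or the first test in a hierarchy, keeps its full alpha. If the sponsor instead split alpha over three tests (0.05/3), a test with 95% power at 0.05 would fall to Φ(1.960 + 1.645 − 2.394) = Φ(1.211), about 89%. The change does not settle the data-dependent choice between t and rank tests, or the handling of patients lost to follow-up; both need their own wording.

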## Ethical aspects

All participants will sign the informed consent, the version of which is being evaluated by the ethics committee of our hospital. The rights of the subjects will be at all times protected by the Declaration of Helsinki. The data will be treated with absolute confidentiality and will be subject to the Data Protection Law 15/1999 of December 13. The nature of the study, the voluntary nature of participation and the proposed objectives will be reported. They may leave the study at any time, if they wish.

## Potential Job Limitations

Due to the natural history of the disease, we cannot foresee decompensations, so there may be losses in the development of the study, having to increase the sample size from the outset.

In this study, since it is a home program, this may be greater due to the lack of stimulation generated by the groups to carry out physical activity.

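### Losses linked to decompensation are expected, but the only answer is a larger sample; the within-arm result may be too favourable and the between-arm result may be biased in either direction

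*Combined protocol and SAP*

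**What the plan says.** Potential Job Limitations names disease-related loss as a risk: "we cannot foresee decompensations, so there may be losses in the development of the study". The remedy given there is to raise enrolment at the start. The section adds that "since it is a home program, this may be greater due to the lack of stimulation generated by the groups"; the word *this* most naturally refers to losses, though the text is loose.

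The Statistical analysis section allows for "a hypothetical loss rate during the study of 15" per cent, not divided by arm or visit, and says "a total of 30 patients per group would be included". It names two families of test:

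- Between groups: the independent-samples t test or Mann-Whitney U. Neither is adjusted for baseline, and the section does not say whether they are applied to visit values or to changes.
- For the effects of rehabilitation: the "t test for related samples when the data follow a normal distribution", with the Wilcoxon signed rank test as the alternative.

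The Method section repeats all baseline measurements at 8 weeks, 6 months and 12 months for both groups. Ethical aspects lets patients leave at any time. The supplied text does not define an analysis population, a method for missing values, a sensitivity analysis, or whether data are collected after a patient stops the programme.

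**The concern.** Decompensation is closely tied to what the trial measures: exercise capacity, symptoms and exacerbations. Loss for that reason cannot safely be treated as unrelated to outcome. With no imputation planned, each named test leaves out a patient who lacks the value it needs. Enlarging the sample replaces the lost numbers but not the lost outcomes, so any bias stays the same size and is estimated more precisely.

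The most exposed result is the one that the plan labels as the effect of rehabilitation, the paired comparison. It has no control arm to cancel a selection effect. The randomised comparison is better protected, because similar selection in both arms largely cancels. That protection fails if the arms lose different proportions of patients, or different kinds of patient.

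**Working it through.** **Inputs from the documents (Statistical analysis section).** 30 per group, 15% loss, 95% power, significance level 0.05 (two-sided assumed; sidedness is not stated). No effect size or SD is given.

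**The plan's own figure.** The 30 per group cannot be confirmed or refuted without an effect size, but it is consistent with the loss allowance: 25/(1 − 0.15) = 29.4, rounded up to 30. With 25 analysed per group, the implied detectable effects are:

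- between groups: (1.960 + 1.645) × √(2/25) = 1.02 SD
- paired, within one arm: (1.960 + 1.645)/√25 = 0.72 SD of the change

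The loss allowance therefore acts on the number analysed and nowhere else.

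**Model for the bias (assumed).** Let each patient's true change have SD 1, and let the tendency to be lost be a normal variable with correlation ρ to a poor change. With a fraction *f* lost, the mean change among retained patients is too high by

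shift(*f*) = ρ × φ(z_f)/(1 − *f*),

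where φ is the standard normal density and z_f its *f* quantile. The factors multiplying ρ are:

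| *f* | φ(z_f) | φ(z_f)/(1 − *f*) |
|---|---|---|
| 10% | 0.1755 | 0.195 |
| 15% | 0.2332 | 0.274 |
| 20% | 0.2800 | 0.350 |

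**Results in SD.** The within-arm column is 0.274ρ. The between-arm column is (0.350 − 0.195)ρ = 0.155ρ. The last column is the within-arm shift divided by 0.15; it shows how much worse lost patients must do than retained ones.

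| ρ | Within-arm, 15% loss | Between-arm, 15%/15% | Between-arm, 20%/10% | Implied gap, lost v. retained, 15% loss |
|---|---|---|---|---|
| 0.2 | 0.05 | 0 | ±0.03 | 0.37 |
| 0.3 | 0.08 | 0 | ±0.05 | 0.55 |
| 0.5 | 0.14 | 0 | ±0.08 | 0.91 |
| 0.8 | 0.22 | 0 | ±0.12 | 1.46 |

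The sign is positive (favouring the programme) if the intervention arm loses 20%, and negative if the control arm does.

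**False-positive rates.** These come from simulation with 30 randomised per arm and no true effect:

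- Paired test, 15% loss, ρ of 0.5 to 0.8: it falsely favours the programme in about 10 to 22% of trials, against a nominal 2.5%.
- Between-group test, equal loss: two-sided error stays at about 5%.
- Between-group test, 20% against 10%: about 5% at ρ = 0.2, about 6% at 0.5 and about 8% at 0.8.
- Between-group test, 25% against 5%: about 5 to 6% at ρ = 0.2, rising to 9 to 16% at 0.5 to 0.8.

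**Cross-check by a simpler route.** If lost patients do worse by a gap *g* that is equal in both arms, the within-arm bias is *f* × *g* and the between-arm bias is (f_I − f_C) × *g*, where f_I and f_C are the loss fractions in the intervention and control arms. With *g* = 0.5: within-arm 0.15 × 0.5 = 0.075 SD; between-arm (0.20 − 0.10) × 0.5 = 0.05 SD; with the imbalance reversed, −0.05 SD. The pattern is the same.

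**The case against.** Four points can fairly be made for the plan.

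1. **The tests.** A reader might infer that every planned test uses complete pairs only. That is not so. The between-group test uses any patient with a value at the visit, and would need both visits only if run on change scores, which the plan does not specify. The plan states no complete-case rule; the omission of patients follows from the tests named.
2. **Who is lost.** A reader might infer that the sickest patients will drop out. The protocol says only that decompensations may lead to losses. No rule withdraws a patient who decompensates, and exacerbations are recorded as an outcome. Worse outcomes among the lost are plausible but remain an assumption.
3. **Direction.** A reader might infer that the randomised comparison will flatter the programme. The documents do not settle this. The remark about the home setting makes greater loss in the intervention arm plausible, but its stated reason is motivation rather than illness. Against it, the intervention arm has weekly support calls and fortnightly gym sessions, while controls have written advice and a call every 15 days. If the programme reduces exacerbations, as hoped, decompensation losses would fall more on controls and the bias would go against the programme.
4. **Size.** Error rates of 9 to 16% need both a five-fold imbalance in loss and a correlation of 0.5 to 0.8.

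All four stand as limits on the point. None of them answers the core: disease-related loss is foreseen, and nothing in the analysis deals with it.

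**Conclusion.** The concern holds in a limited form, and the analysis section should be changed. The within-arm paired result is optimistic if lost patients do worse, even with equal loss: about 0.05 to 0.08 SD under mild dependence and 0.14 to 0.22 SD under strong dependence, at the plan's own 15% loss. The between-arm result is about unbiased with equal loss and an equal gap, and otherwise may err either way, by about 0.03 to 0.12 SD at 20% against 10%. These shifts are modest beside the difference of roughly 1 SD that the sample size implies. They matter most for a borderline result, and for any claim of benefit that rests on the paired test. Only the 15% overall loss and the 30 per group come from the documents; every correlation, gap and arm-specific rate is an assumption.

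**What to change.** In the Statistical analysis section:

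1. Define the primary population as all randomised patients in their assigned group.
2. Make the between-arm comparison the primary test of the programme, using one repeated-measures mixed model (arm, visit, arm-by-visit, baseline value) on every observed visit. Report the paired within-arm changes as descriptive.
3. State that patients who stop the programme, and who still consent, continue to be invited to Visits 3 to 5.
4. Record the reason for each loss and report it by arm.
5. Add one sensitivity analysis that shifts the missing values in each arm separately, in both directions, until the conclusion changes.

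Items 3 and 5 are needed because the mixed model assumes data missing at random. It does not generally remove bias when loss depends on outcomes that were never seen, and it adds little for a patient with no visit after baseline. Shifting both arms in both directions avoids presuming which way the bias runs.

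The cost is a change of wording, a little more analysis (mixed models are available in SPSS, the planned software), and some staff effort to invite patients who stopped the programme. The visits themselves are already scheduled.
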